For data coded according to WHO-DD (e.g., concomitant medications), summaries will be done on the preferred term level where the preferred term is corresponding to codes ending in 01001. With this approach, variations of salt forms of active ingredients will be analyzed under the same term, e.g. diphenhydramine and diphenhydramine hydrochloride will be analyzed as the same preferred term diphenhydramine.

Data collected after reinitiated treatment:

Data collected after reinitiation of treatment will be included in the summary statistics. Data listings will include both data collected during the first period of treatment, and during the reinitiation of treatment (except for listings displaying parameters derived during the first treatment period only). Data collected during the reinitiation of treatment will be flagged.

Re-screened participants

Re-screened participants will be only counted once in the screening analysis set, considering the latest screening (screening with latest informed consent). If a participant is re-screened several times, then he will be counted only once in the disposition table in the number of re-screened participants.

Definition of Pre-, During-, Post-pandemic Time Periods

Participants will be categorized based on the COVID-19 study period defined as:

- Pre-pandemic time period: subjects who started the treatment before the start of COVID-19 pandemic.
- During-pandemic time period: subjects who started the treatment on the same date or after the start of COVID-19 pandemic
- Post-pandemic time period: the end of pandemic is considered not yet reached anywhere at the time of this IAP version redaction, consequently no participant will be grouped into the post COVID-19 study period for this study and no post-pandemic date will be defined.

The start of COVID-19 pandemic is defined by country as the earliest date of either the date of the first death from COVID-19 occurred in each country according to the published data by European Centre for Disease Prevention and Control on 26th June 2020 (<https://www.ecdc.europa.eu/en/publications-data/download-todays-data-geographic->

distribution-covid-19-cases-worldwide) or 11th March 2020 (when the WHO declared COVID-19 pandemic).

Software:

All analyses will be performed using SAS 9.4 or higher in the SAS Grid environment.

10 Study Participants

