10.1 Disposition of Participants and Discontinuations

Descriptive statistics will be used to summarize participant disposition and reason for discontinuation, based on the electronic case report form (eCRF) data.

The following information will be reported:

- Total number of participants prescreened
- Number of participants who did not continue beyond prescreening overall and grouped by reason (reason related to central testing, reason related to local testing, reason independent of local/central testing)
- Number of participants who completed the pre-screening (pre-screening ICF signed), but have not signed the main ICF yet
- Total number of screened participants
- Total number of re-screened participants
- Number of participants who did not continue beyond screening overall and grouped by reason (participant did not meet all eligibility criteria, withdrew informed consent, progressive disease, adverse event, lost to follow-up, death, other)
- Number of participants who completed the screening (main ICF signed), but have not been randomized yet
- Number of randomized participants overall and by treatment arm
- Number of randomized participants who did not receive any treatment
- Number of randomized participants with treatment on-going in each treatment arm
- Number of randomized participants off treatment, grouped by treatment arm and main reason
- Number of randomized participants with treatment reinitiated
- Number of randomized participants with treatment on-going after reinitiation
- Number of randomized participants who discontinued treatment after reinitiation

- Number of randomized participants who discontinued the treatment but are still in study for follow-up, grouped by treatment arm
- Number of randomized participants who discontinued the study, grouped by treatment arm and main reason (as reported on “Study termination” page of the eCRF).

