12.5 Anticancer Treatment after Discontinuation

Anticancer treatment after discontinuation of IMP will be summarized according to the eCRF page “Anticancer Treatment After Discontinuation” for anticancer drug therapy, “Radiotherapy After Discontinuation” for anticancer radiotherapy and to “Surgery After Discontinuation” for anticancer surgery.

The number of participants in each of the following anticancer treatment categories will be tabulated:

- Participants with at least one subsequent anticancer treatment (i.e. drug therapy, radiotherapy or surgery)
- Participants with at least one subsequent anticancer drug therapy
- Participants with at least one subsequent anticancer radiotherapy
- Participants with at least one subsequent anticancer surgery.

The type of subsequent anticancer drug therapy as provided in the e-CRF (i.e. Cytotoxic therapy/ Endocrine therapy/ Monoclonal antibodies therapy/ Small molecules/ Immunotherapy/ Other) will

be described, as well as the intent of therapy (Neoadjuvant/Adjuvant) and the best response (CR, PR, stable disease, PD, non-CR/non-PD, not evaluable, unknown).

In addition, the anticancer treatment after discontinuation of IMP will be provided in a data listing including type of therapy, preferred term/medication name, medication type, regimen name, best response, start date, end date, radiotherapy site and name of surgery/location.

13 Treatment Compliance and Exposure

Summaries will be performed on SAF analysis set.

Participants will be treated with bintrafusp alfa or pembrolizumab at the following doses:

- Bintrafusp alfa at a dose of 1200 mg per infusion once every 2 weeks
- Pembrolizumab at a dose of 200 mg per infusion once every 3 weeks.

These doses will be administered as “flat” doses independent of the body weight. Both treatments will be administered until PD per RECIST 1.1, unacceptable toxicity, or for up to 24 months.

All dosing calculations and summaries will be based on “Study Treatment Administration Details” eCRF page. Data collected during the treatment reinitiation phase will be included in the summary statistics.

A dose is regarded to be administered, if the actual dose received is > 0

The duration of bintrafusp alfa treatment (in weeks) during the study is defined as:

$$\text{duration} = \left(\frac{\text{date of last dose} - \text{date of first dose} + 14}{7} \right)$$

with “last dose” being the last dose of reinitiation period, if applicable.

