The duration of pembrolizumab treatment (in weeks) during the study is defined as:

$$\text{duration} = \left(\frac{\text{date of last dose} - \text{date of first dose} + 21}{7} \right)$$

with “last dose” being the last dose of reinitiation period, if applicable.

The cumulative dose of bintrafusp alfa or pembrolizumab per participant in a time period is the sum of the actual dose levels that the participant received within that period (i.e. total dose administered (mg)).

The dose intensity (DI) (mg/cycle) of bintrafusp alfa per 2-week period is defined as:

$$\text{dose intensity} = \left(\frac{\text{Cumulative dose}}{(\text{duration of therapy (in weeks)})/2} \right)$$

The dose intensity (DI) (mg/cycle) of pembrolizumab per 3-week period is defined as:

$$\text{dose intensity} = \left(\frac{\text{Cumulative dose}}{(\text{duration of therapy (in weeks)})/3} \right)$$

The relative dose intensity (RDI) is defined as the actual dose intensity divided by the planned dose per cycle and expressed in percentage.

$$\text{RDI (\%)} = 100 * [\text{DI (mg/cycle)} / (\text{planned dose per cycle (mg)})]$$

For participants who reinitiate the treatment, the varying duration of cycle will be taken into account.

The following summary tables will be provided:

- Duration of therapy (weeks)
- Total number of infusions received overall
- Cumulative dose (mg)
- Dose intensity (mg/cycle)
- Relative dose intensity (%).

A listing of treatment exposure will include treatment arm, participant identifier, age, sex, race, visit, infusion start date and time, infusion end date and time, infusion rate (mL/hr), actual dose (mg), administration location, administration modification and reason for modification, change in administration detail, treatment delay (days). This listing will be sorted by treatment arm, participant identifier, infusion start date and infusion end date.

An additional listing of treatment exposure will include treatment arm, participant identifier, age, sex, race, duration of therapy (weeks), total number of infusions received, cumulative dose of therapy (mg), dose intensity (mg/cycle), and relative dose intensity (%). This listing will be sorted by treatment arm and participant identifier.

Therapy Delays

Delays of therapy will be derived by infusion as follows:

- For bintrafusp alfa interventions as the no. of days since last infusion - 14
- For pembrolizumab interventions as the no. of days since the start of last infusion – 21.

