If the value above is >0 days, then this will be classed as a delay. A participant may have more than one treatment delay throughout the course of treatment.

The following will be summarized in a table:

- Number of participants with delays
- Longest delay per participant (no delay, 1-2 days, 3-8 days, 9-15 days, ≥16 days)
- Number of delays per participant (0 delay, 1 delay, 2 delays, 3 delays, ≥ 4 delays).

Infusion Temporary Interruptions

IMP infusion interrupted as recorded on the “Study Treatment Administration Details” page of the eCRF will be used for analysis. Number of participants with at least one IMP interruption, reason for infusion temporary interruptions, as well as a categorization of the number of IMP interruptions (1 / 2 / ≥ 3) will be summarized.

Infusion Rate Reductions

Infusion rate reductions as recorded on the “Study Treatment Administration Details” page of the eCRF will be used for analysis. Number of participants with at least one infusion rate reduced to 50%, reasons for infusion rate reduction, as well as a categorization of the number of infusion rate reductions (1 / 2 / ≥ 3) will be summarized.

14 Efficacy Analyses

Best Overall Response efficacy analyses at OR interim analysis will be performed on 73-10 PD-L1 High analysis set, if any Best Overall Response sensitivity analyses will be performed at OR interim analysis it will be based on FAS with 6m f-up analysis set. Remaining efficacy analyses will be presented for the FAS analysis set.

A group sequential testing procedure will be used to test primary endpoints. CCI

14.1 Best Overall Response According to RECIST 1.1 as Assessed by IRC (Secondary Endpoint)

Best overall response (BOR) will be assessed based on the tumor response at different evaluation time points from randomization until the first documented disease progression for RECIST 1.1 criterion. Only tumor assessments performed before the start of any further anticancer treatment will be considered in the assessment of BOR. Clinical deterioration will not be considered as documented disease progression.

The BOR according to RECIST 1.1 criteria as assessed by IRC can be CR, PR, Non-CR/Non-PD, SD, PD, or NE.

The following rules will be applied to the derivation of BOR:

- CR = at least one determination of CR before disease progression
- PR = at least one determination of PR before disease progression (and not qualifying for a CR)

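### For participants who re-initiate treatment, SAP Section 13 counts the drug-free gap as treatment duration and scores the restart as a delay; separately, the IRR resolution window differs between protocol and SAP

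*SAP*

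**What the plan says.** Protocol Section 7.1 allows one re-initiated course, for example when disease progresses after treatment was stopped in response or stable disease, or when an adverse event that led to discontinuation has resolved. It sets no maximum gap.

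SAP Section 13 then gives these rules:

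- **Duration.** Last dose date minus first dose date, plus 14 days (bintrafusp alfa) or 21 days (pembrolizumab), divided by 7. In both arms the last dose is defined as "being the last dose of reinitiation period, if applicable".
- **Inclusion.** "Data collected during the treatment reinitiation phase will be included in the summary statistics".
- **Dose intensity (DI) and relative dose intensity (RDI).** Both rest on this duration, with one qualification: "For participants who reinitiate the treatment, the varying duration of cycle will be taken into account". No formula follows.
- **Delays.** The rule for one arm reads "For bintrafusp alfa interventions as the no. of days since last infusion - 14". The pembrolizumab rule has the same form, with 21 subtracted in place of 14. A threshold is then set for both arms: "If the value above is >0 days, then this will be classed as a delay". The table shows the longest delay per participant, with a top category of 16 days or more.

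SAP Section 10.1 treats stopping and restarting as separate dispositions and reports the "Number of randomized participants with treatment reinitiated".

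On signs and symptoms of IRRs, both documents require onset on the day of infusion. Protocol Section 6.9.1 accepts an end date up to 2 days after onset. SAP Section 15.2.3.1 accepts only the day of infusion or the next day.

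**The concern.** Someone who has been recorded as off treatment and later restarts was not being treated in between. The duration formula says otherwise, and the delay rule turns a discontinuation into a late infusion. Duration and dose intensity are among the outputs that SAP Section 6.6 keeps for the single report after trial discontinuation, so a reader of that report would see treatment time that was not given. If the delay table is produced, that reader would also see delays that were really discontinuations.

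The IRR mismatch is a separate matter. IRRs are adverse events of special interest, which Section 6.6 also keeps. The same event can be an IRR under one document and not under the other.

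**Working it through.** The documents state no figure to reproduce here, so the SAP formulas were applied to assumed dosing histories with no missed dose. The doses and intervals (1200 mg every 2 weeks, 200 mg every 3 weeks) are from SAP Section 13. The schedules and gap lengths are assumptions.

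**Baseline check without re-initiation.** With 26 bintrafusp alfa infusions on schedule, the last is on day 350: (350 − 0 + 14)/7 = 52 weeks. With 17 pembrolizumab infusions, the last is on day 336: (336 − 0 + 21)/7 = 51 weeks. RDI is 100% and there are no delays, so the formulas behave as intended.

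**Bintrafusp alfa, 26 weeks on / 26 off / 26 on.** Doses on days 0 to 168 and 364 to 532, 26 infusions in all.

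- SAP duration: (532 − 0 + 14)/7 = 78 weeks.
- Sum of courses: (168 − 0 + 14)/7 + (532 − 364 + 14)/7 = 26 + 26 = 52 weeks.
- Delay at restart: (364 − 168) − 14 = 182 days.
- Cumulative dose: 26 × 1200 = 31200 mg. Over 78 weeks, DI = 31200/(78/2) = 800 mg per cycle and RDI = 66.7%. Over 52 weeks, DI = 31200/(52/2) = 1200 mg per cycle and RDI = 100%. Section 13 does not say which denominator its promised adjustment produces.

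**Pembrolizumab, 24 weeks on / 24 off / 24 on.** Doses on days 0 to 147 and 336 to 483.

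- SAP duration: (483 − 0 + 21)/7 = 72 weeks.
- Sum of courses: 2 × (147 + 21)/7 = 48 weeks.
- Delay at restart: (336 − 147) − 21 = 168 days.

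**Range of gaps.** For a participant with 78 weeks on drug over two courses (26 + 13 bintrafusp alfa or 17 + 9 pembrolizumab infusions), the results are the same in both arms:

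| Gap (weeks) | SAP duration (weeks) | Delay scored (days) |
|---|---|---|
| 4 | 82 | 28 |
| 12 | 90 | 84 |
| 26 | 104 | 182 |
| 52 | 130 | 364 |

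Every delay in the table falls in the top category. A restart reaches that category once the interval between infusions is 14 + 16 = 30 days (bintrafusp alfa) or 21 + 16 = 37 days (pembrolizumab).

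**Arm level.** Mean duration rises by the proportion re-initiating times the gap. For 1% with a 26-week gap: 0.01 × 26 = 0.26 weeks. For 1% to 10% with gaps of 12 to 52 weeks, the range is 0.01 × 12 = 0.12 to 0.10 × 52 = 5.2 weeks. Both the proportion and the gap are assumptions.

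**IRR window.** Take onset on the infusion day as day 0. The protocol accepts an end date on day 0, 1 or 2; the SAP accepts day 0 or 1. An event ending on day 2 is an IRR sign or symptom under the protocol and not under the SAP.

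**The case against.** **The duration rule is a declared convention.** Section 13 states it outright, and it matches the on-treatment period in SAP Section 9, which also runs through both courses. That is fair as to intent. But the continuous on-treatment period has a purpose, which is to keep adverse events arising in the gap in the treatment-emergent tables. A duration of therapy has no such need, and the SAP's own disposition rules record the participant as off treatment in that time.

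**Removing only restart gaps is uneven.** Holds and skipped doses also count as elapsed time, and protocol Section 6.8.2 allows up to 12 weeks for some adverse reactions to recover. A long hold would stay in the duration while a shorter discontinue-and-restart gap would leave it. This stands as a limitation. The boundary is still workable, because discontinuation and re-initiation are recorded events.

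**The delay effect is limited.** The top category hides the 182- and 168-day values, and ordinary holds also fill it. Section 6.6 lists exposure outputs only as examples and does not name the delay table. So this part matters only if the table is produced.

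**Other outputs help.** "Data collected during the reinitiation of treatment will be flagged" in the listings, and Section 10.1 provides a listing of re-initiators with their dates. Cumulative dose and number of infusions are unaffected by the gap. The affected participants can be found, but the summary tables do not separate them.

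**The IRR wording sits outside the statistics section.** The SAP is based on protocol Section 9, so the absence of this difference from SAP Section 7 is weak evidence of an undeclared analysis change. The two definitions still conflict.

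Two stronger readings are tempting, and the documents do not support them. A reader might infer that RDI will be reported at 67% for the example participant; Section 13 promises an adjustment, so this shows missing detail and no established error. A reader might also infer that the gap dilutes the exposure-adjusted incidence rates in SAP Section 15.2.5. That rests on an adverse event summarization period that the SAP does not define, in an analysis that Section 6.6 does not name. Treatment-emergent events in the gap would also count, so events and time would cover the same window.

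**Conclusion.** The point holds as a minor one, confined to descriptive exposure and safety outputs. As written, Section 13 counts the whole drug-free gap as treatment for every re-initiator: 78 weeks against 52, or 72 against 48, in the assumed examples. It also scores nearly every restart as a delay of 16 days or more, which matters if the delay table is produced. The IRR definitions differ by one day for events with onset on the infusion day. Such events stay in the general treatment-emergent tables and only their IRR classification changes.

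The per-participant figures rest on assumed schedules. The arm-level effect cannot be determined, because the documents give no re-initiation rate or gap lengths, and it may be small. Primary endpoints, alpha and power are unaffected.

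**What to change.** 1. For re-initiators, define duration as the sum of the two courses, each with its own added 14 or 21 days, and use that sum as the DI and RDI denominator. This writes out the adjustment that Section 13 promises. State that holds and skipped doses within a course are counted as now.
2. Start the delay derivation anew at the first infusion of the re-initiated course.
3. Reconcile protocol Section 6.9.1 with SAP Section 15.2.3.1 so that both use one resolution window for IRR signs and symptoms, or declare the difference in SAP Section 7.

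The cost is SAP wording, two derivations and one reconciled definition. No new data are needed, since dose dates and re-initiation are already collected.

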14.4.3 Time to Follow-up for PFS

A Kaplan-Meier analysis for PFS follow-up duration will be generated to assess the follow-up time in the treatment arms reversing the PFS censoring and event indicators.

Kaplan-Meier estimates will be presented by treatment arm together with the median time of follow-up for PFS. In particular, the follow-up rate at 3, 6, 9, 12 and 24 months will be estimated with corresponding two-sided 95% CIs.

CCI

CCI

CCI

14.8 Duration of Response (Secondary Endpoint)

Duration of response (DOR) is defined as the time from first documentation of objective response (CR or PR) to the date of first documentation of objective progression of disease (PD) or death due to any cause whichever occurs first. The analysis of DOR will be performed on unconfirmed objective response of CR or PR according to RECIST 1.1 as adjudicated by IRC. The censoring rules for DOR are as described above for PFS. The number of participants with ongoing response will be described as the number of censored participants with administrative censoring.

$DOR = (\text{date of PD or death/censoring} - \text{date of objective response} + 1) / 30.4375$ (months).

The analysis of DOR will be performed with a Kaplan-Meier method (product-limit estimates) and a summary of associated statistics will be presented including corresponding two-sided 95% CIs. The CIs for the median will be calculated according to Brookmeyer and Crowley (1982) and CIs for the survival function estimates at Month 3, 6, 9, 12 and 24 will be derived using the log-log transformation according to Kalbfleisch and Prentice (1980) (CONFTYPE=loglog default option in SAS PROC LIFETEST). The estimate of standard error will be computed using Greenwood's formula.

The time and duration of response per participant may also be displayed in a swimmer graph in participants with unconfirmed CR/PR (delayed response is also considered).

A participant listing will provide the following information: treatment arm, participant identifier, age, sex, race, date of randomization, date of first response, time to response, date of last tumor assessment, censored (Y/N), date of event/censoring, event/censoring reason, DOR.

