7.2 Participant Discontinuation/Withdrawal from the Study

A participant must be withdrawn in the event of any of the following:

- A participant may withdraw from the study at any time, at his/her own request or may be withdrawn at any time at the discretion of the Investigator for safety, behavioral, compliance, or administrative reasons.

Section 1.3 (Schedule of Activities) specifies the data to collect at study discontinuation and follow-up, and any additional evaluations that need to be completed.

In case of withdrawal from treatment, the day of End-of-Treatment will correspond to the day of withdrawal (or within 7 days). The assessments scheduled for this visit should be performed, if possible, with focus on the most relevant assessments. In case participant gets enrolled into new study or any new therapy post withdrawal from study, the Safety Follow-up Visit should be scheduled prior to start of the new treatment irrespective of the 28-day safety follow-up period. In either case, the appropriate eCRFs for the End-of-Treatment Visit must be completed. In case of withdrawal, participants will be asked to continue safety and survival follow-up, which includes the collection of data on survival and subsequent anticancer therapy. After completion of the Follow-up period or after the End-of-Treatment Visit, whichever is applicable, the appropriate eCRF section for Study Termination must be completed.

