Neither progressed nor died	Censored	Date of last evaluable tumor assessment with outcome CR, PR or SD or date of randomization, whatever is later

The last tumor assessment date is defined as the last available and evaluable tumor assessment performed prior to the cutoff date (or prior to end of study, i.e. participants lost to follow-up or who withdraw consent) or prior to subsequent anticancer therapy (i.e. drug therapy, radiotherapy or surgery). If no evaluable tumor assessment is available, this date will be the randomization date.

$PFS = (\text{date of PD or death/censoring} - \text{date of randomization} + 1) / 30.4375$ (months).

Kaplan-Meier analysis

The analysis of PFS will be presented by treatment arm and will be performed with a Kaplan-Meier method (product-limit estimates) and a summary of associated statistics will be presented including corresponding two-sided 95% CIs. The CIs for the median will be calculated according to Brookmeyer and Crowley (1982) and CIs for the survival function estimates at Month 3, 6, 9, 12 and 24 will be derived using the log-log transformation according to Kalbfleisch and Prentice (1980) (CONFTYPE=loglog default option in SAS PROC LIFETEST). The estimate of standard error will be computed using Greenwood's formula.

Frequency (number and percentage) of participants with and without an event, overall and per event type (PD or death) will be presented by treatment arm. Censoring reasons will be described by treatment arm, as follows:

- Administrative censoring (ongoing in the study without an event)
- No baseline assessment
- No evaluable post-baseline assessment
- Start of new anticancer therapy
- Event after 2 or more missing or non-evaluable post-baseline assessments
- Withdrawal of consent
- Lost to follow-up

Lost to follow-up will include the following participants:

- Lost to follow-up status is collected on the eCRF treatment termination page or eCRF study termination page prior to the analysis cutoff;
- Participants with last known alive date > 14 weeks prior to the analysis cutoff date (duration of 14 weeks is based on the assessment schedule of every 3 months for survival follow-up interval + 1 week window).

A participant listing will be also provided with the following information: treatment arm, participant identifier, age, sex, race, randomization date, date of last tumor assessment, date of event/censoring, event/censoring reason, time to event.

Log-rank test

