14.11 Overall Survival (Primary Endpoint)

The overall survival (OS) time is defined as the date from randomization to death due to any cause:

$OS = (\text{date of event/censoring} - \text{date of randomization} + 1) / 30.4375$ (months).

For participants alive at the time of data cutoff date or who are lost to follow up, OS will be censored at the last date known to be alive.

The date of event / censoring is defined in [Table 8](#).

Table 8 Survival Event / Censoring

Survival status	Date of event / censoring	Censoring
Participants alive or lost to follow-up before or at cutoff date	Last date known to be alive	Yes
Participants who died before or at cutoff date	Date of death	No

The following complete dates will be used to determine the last date known to be alive. Only the ones among them that are before or at data cutoff and which are not imputed shall be used in the derivation. Dates past the data cutoff will be ignored by the derivation:

- All participant assessment dates (blood draws (laboratory, PK), vital signs, performance status, ECG, tumor assessments, PRO assessments)
- Start and end dates of anticancer therapies administered after IMP discontinuation.
- AE start and end dates
- Last known alive date collected on the ‘Survival Follow-up’ eCRF (do not use follow-up date)
- IMPs start and end dates (including reinitiation of treatment)
- Randomization date
- Completion/Discontinuation date from the “Study Termination” eCRF page (do not use if reason for discontinuation is lost to follow-up or death)

Only dates associated with actual examinations of the participant reported in the eCRF will be used in the derivation. Dates associated with a technical operation unrelated to participant status such as the date a blood sample was processed will not be used.

The analysis of OS time will be performed with a Kaplan-Meier method with the same approach described for PFS in Section 14.4. Kaplan-Meier estimates (product-limit estimates) will be presented together with a summary of associated statistics including corresponding two-sided 95% CIs. They will be estimated at 12, 18, 24, 30, 36, 42, and 48 months.

A Cox’s regression model will be used with the same approach as for PFS described in Section 14.4.

The following null hypothesis will be tested:

$$H_0^{OS}: \lambda_M^{OS}(t) = \theta \lambda_P^{OS}(t), \theta \geq 1 \text{ versus } H_1^{OS}: \lambda_M^{OS}(t) = \theta \lambda_P^{OS}(t), \theta < 1$$

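### SAP 14.8 counts a response as ongoing with no limit on the age of the last scan, so a responder whose imaging has stopped can be reported as still responding

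*SAP*

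**What the plan says.** SAP 14.8 takes its rules from the PFS section: "The censoring rules for DOR are as described above for PFS". It then fixes the descriptive count: "The number of participants with ongoing response will be described as the number of censored participants with administrative censoring".

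SAP 14.4 lists seven reasons for censoring, to be tabulated by arm. The first is "Administrative censoring (ongoing in the study without an event"). The only reason that concerns missed scans is "Event after 2 or more missing or non-evaluable post-baseline assessments". Loss to follow-up is assigned either from the eCRF status or by a rule on vital status: "Participants with last known alive date > 14 weeks prior to the analysis cutoff date".

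SAP 14.11 names the sources for the last date known alive. One of them is "Last known alive date collected on the ‘Survival Follow-up’ eCRF". Protocol 4.1 plans survival contact every 12 weeks and allows it by telephone. SAP 10.1 treats people who are off treatment as still in the study, because it tabulates "Number of randomized participants who discontinued the treatment but are still in study for follow-up, grouped by treatment arm".

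**The concern.** A response is ongoing at cutoff if recent imaging shows no progression. The SAP's count asks something else: whether the person is still in the study with no recorded event. The two agree while scans continue on schedule. They part when imaging stops but survival contact goes on.

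Two outputs are at stake. One is the number of ongoing responses, a figure commonly read alongside the DOR curve. The other is the table of PFS censoring reasons by arm. In an open-label trial, readers use that table to judge whether loss of assessment differs between arms. As written, it merges people scanned on schedule up to the cutoff with people whose scans ended long before. For PFS this applies to every participant without an event, not only to responders.

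**Working it through.** **Classification.** There is no figure in the plan to reproduce, so this part is by elimination. Take a responder with no PD, death, new anticancer therapy or consent withdrawal, no further scans, and a survival contact within 14 weeks of cutoff. Going through the reasons in SAP 14.4:

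| Reason | Does it apply? |
|---|---|
| No baseline assessment | No: a responder has one |
| No evaluable post-baseline assessment | No: the response is one |
| New anticancer therapy | No |
| Event after missed assessments | No: it needs a later event |
| Withdrawal of consent | No |
| Lost to follow-up | No, unless the eCRF records it: the survival contact keeps the alive date recent |
| Administrative | Yes: the only one left |

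The length of the scan gap plays no part. Illustration with assumed dates: last scan, showing PR, at month 6; survival call 4 weeks before a month-24 cutoff. The gap is 18 × 30.4375 ≈ 548 days, and the response counts as ongoing. Yet the SAP 14.4 censoring rules decline to accept a later event after 84 days without assessment in the first 18 months of follow-up, or 168 days after that.

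**Size, under assumptions.** None of these inputs is in the documents: uniform accrual over 24 months, cutoff at month 30, response 3 months after randomization, exponential DOR with median 18 months, and a constant yearly probability r of stopping scans. The time T from response to cutoff is then uniform on 3 to 27 months.

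Let λ = ln 2/18 = 0.0385 per month, μ = −ln(1 − r)/12, s = λ + μ, and g = 84/30.4375 = 2.76 months.

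- Counted as ongoing: mean over T of e^(−sT) + (μ/s)(1 − e^(−sT)).
- Of these, no scan in the last 84 days: mean over T of (μ/s)(1 − e^(−s(T−g))).

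For r = 10%: μ = 0.00878, s = 0.0473, μ/s = 0.1857, and the mean of e^(−sT) is (0.8677 − 0.2789)/(24 × 0.0473) = 0.5188.

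- Ongoing: 0.5188 + 0.1857 × 0.4812 = 0.608.
- Out of date: 0.1857 × (1 − 0.5188 × e^(0.0473 × 2.76)) = 0.1857 × 0.4088 = 0.0759.
- Share: 0.0759/0.608 = 12.5%.

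| r per year | No scan within 84 days | Using the 84/168-day limits |
|---|---|---|
| 5% | 6.4% | 5.9% |
| 10% | 12.5% | 11.6% |
| 15% | 18.3% | 17.0% |

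**Effect of the omitted exits.** In this model, at r = 10%, unscanned people who have already progressed make up 0.0260 of all responders in the out-of-date group and 0.0267 in the whole ongoing count. Some of them would die or start new therapy before cutoff, and SAP 14.4 then gives them another reason. If half do, the share becomes (0.0759 − 0.0130)/(0.608 − 0.0134) = 10.6%. If 80% do, it becomes (0.0759 − 0.0208)/(0.608 − 0.0214) = 9.4%.

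**The case against.** The strongest reply is that nothing inferential depends on this label, and that is right. DOR and PFS are censored at the last evaluable tumor assessment, so unscanned time earns no credit in the curves, medians or landmark rates. The log-rank test and the Cox model do not use the censoring reason. A reader might infer that the DOR median or the PFS hazard ratio is distorted by this rule; the documents do not support that.

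A reader might also infer that loss of imaging is hidden. That goes too far. SAP 14.4.3 plans a reverse Kaplan-Meier of PFS follow-up by arm, which shortens in an arm that loses scans early. The PFS and DOR listings give each participant's last tumor assessment date and censoring reason. SAP 10.1 counts missed and delayed tumor assessments related to COVID-19 by arm. These reveal loss of imaging only in part: none isolates it in a summary, and the ongoing count uses none of them.

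Nor do the documents show that scans usually end with treatment. Protocol 7.2 says that after withdrawal "participants will be asked to continue safety and survival follow-up", without naming imaging in that sentence, but it also refers to the schedule of activities. Protocol 8.1 times scans from first dose, and Protocol 7.1 expects regular scans in people who may reinitiate treatment. The imaging rows of the schedules cannot be read in the public copy. Continued scanning would reduce the number affected; it would not change how anyone who misses scans is classified.

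Finally, not every responder who stops scanning is miscounted. Those who start new therapy, withdraw consent, or progress or die after the gap receive other reasons.

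**Conclusion.** The point holds as a defect in a descriptive rule. SAP 14.8 lets a response count as ongoing on the strength of survival contact alone, however old the last scan, and the PFS censoring table carries the same ambiguity. The classification follows from the visible text, although the SAP gives no order of precedence among the reasons.

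The size is not known. In principle it runs from none to all of the administratively censored responders. The 6% to 18% rests entirely on the assumed dropout, DOR and accrual, and is an upper-side figure. The same model puts true progression at about 34% of the out-of-date cases (0.0260/0.0759), and a reader might take that as a finding. It is not one: with 50% or 80% of those people leaving through death or new therapy, it falls to about 21% (0.0130/0.0629) or 9% (0.0052/0.0551).

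The study was discontinued after the PFS interim analysis, but SAP 6.6 keeps DOR and IRC-assessed PFS in the analysis for reporting. The clarification still matters for what is published, though no decision depends on it. It is worth considering rather than essential.

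**What to change.** In SAP 14.8, count a response as ongoing only if there is no event, no new anticancer therapy has started, and the last evaluable IRC assessment lies within two scheduled intervals before cutoff: 84 days, or 168 days after 18 months of follow-up. These limits already stand in SAP 14.4.

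In SAP 14.4, split administrative censoring into two lines by arm: on schedule at cutoff, and no evaluable assessment within two scheduled intervals before cutoff.

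The cost is a few lines of SAP text and one variable derived from scan dates already collected. No test or estimate changes. The drawback is a slightly lower reported number of ongoing responses.
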